- Subjects will meet Rome IV criteria for functional nausea, irritable bowel syndrome, dyspepsia or functional abdominal pain as determined by a pediatric gastroenterologist
- Patients must have an intact external ear that is free of infection or severe dermatological conditions, have stable vital signs for their respective age, no history of seizures and no currently implanted electrical device

Exclusion Criteria:

- Mental retardation or pervasive developmental disorder or epilepsy
- Psychosis
- Genetic or chromosomal disorders
- Pregnancy
- Subjects who admit to substance abuse during screening
- Patients with findings of peptic ulcer disease, H.pylori gastritis, celiac disease, inflammatory bowel disease, allergic disorders, or any chronic condition or medication that may cause nausea or pain
- Patients who are treated with opioids or who had any changes in their medical regimen in the past four weeks prior to study
- Patients with a history of allergy to adhesives

Study Design Overview

Subjects will undergo medical workup per standard of care. Subjects refractory to current medical therapy may be enrolled without changes to their current medical treatment. No new pharmacological agents will be added during the 4-week study period and no changes in dosing or scheduling of current therapy will be allowed during the study period. Subjects will be screened weekly for any side effects by registered nurses who are part of the Pediatric Translational Research Unit (pTRU). All subjects will be asked to notify the PI or research team with any worsening in symptoms or side effects of therapy. If symptoms worsen or fail to improve during the study or if their clinical presentation changes in any way, subjects will have the option to drop out any time, receive standard medical therapy and appropriate referrals. If per standard of care, a subject requires a change in one or several of their regular medications during the study, they will be asked to notify the research team. To monitor this, the subjects will be inquired about their medication list and doses during their weekly visits. If the medication change is determined to potentially affect the study results, the subject may be excluded from further study as determined by the PI.

Protocol and Procedures

Pre (Baseline):

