At the time of each EAD placement, a member of the research team will inquire and document current medications and doses and if subjects experienced any side effects from the EAD during the previous week. Subjects will also be asked if they wore the device for all five days and it will be documented if the device was returned to the research team.

Demographic Information

Data will be collected as part of the clinic visit and at enrollment. This includes child's date of birth, age, sex, ethnicity, and caretaker marital status. The physician assessment will also include questions about prior medical diagnoses, co-morbid symptoms and the characteristics of pain and nausea such as timing and triggers. The FDI will be performed at visit 1; 4 and 5. This instrument has demonstrated reliability and validity and have been used for both clinical and research purposes in pediatric populations.

Medical Information

Information recorded for patients is part of clinical care and includes weight, height, vital signs, medications, gastrointestinal symptoms, early life events, family history, surgeries and other medical co-morbidities.

[figure not shown]
Heart Rate Variability

HRV reflects the variability of the R-R interval in the electrocardiogram and its frequency domains (30). HRV is an indirect measure of central autonomic control and an indicator of overall psychological well-being (31). Reductions in resting HRV reflect decreases in vagal output. The high frequency range of HRV is considered representative of vagal (parasympathetic) activity and studies show altered vagal tone as measured by HRV in subjects experiencing nausea (32). All subjects will undergo a 10 minute baseline HRV measurement (five minutes supine and 5 standing) after 10 minutes of rest. Recordings will be performed supine and standing to assess baroreflex response. HRV indices such as high and low frequency domains, low/high frequency ratio and the time domain RMSSD as a surrogate of vagal tone (30) will be analyzed using Kubios software. The RMSSD values will be the primary HRV outcome and compared to baseline (pre-EAD stimulation), post-stimulation and 2-3 month later at follow up.

We will use the following HRV collection methods; *eMotion* Faros ECG Mobile 360 and the Actiwave by CamNTech. The *eMotion* Faros will primarily used, and in the event that the faros devices are not available, the Actiwave will be available as a backup device.

eMotion Faros ECG Mobile 360

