4. The subject will be advised not to immerse the device in water as the device is water resistant but not water proof. If showering or washing their hair, subjects will be instructed to place a dry wash cloth or plastic such as Press n' seal over the area to help protect the device. Subjects will be given a contact person (primary investigator and research coordinator) to call if they are having any problems with the device or if it falls off.
5. The patient will be instructed on removing the device after 5 days. If not comfortable doing so or unable to carry out the instructions, the patient may be seen that day for removal by one of the investigators.
6. The patient will be asked to return the used device for proper disposal when they return for their follow-up appointment.
7. The subject will be given a handout with information (attached) on device handling, exact date and time of device removal and date and time to return.
8. The subject will be advised to refrain from using any new or as needed anti-emetic or pain medications.
9. The subject is dismissed.

G. RISK CATEGORY

45 CFR 46.405- Research involving greater than minimal risk but presenting the prospect of direct benefit to the individual child subjects involved in the research.

H. RISKS AND THE PRECAUTIONS WHICH WILL BE TAKEN TO MINIMIZE RISK EXPOSURE

Safety Data

All safety variables (e.g., adverse events will be summarized for each assessment time (including follow-up) using descriptive statistics. Incidence of adverse events will be summarized by treatment.

Heart Rate Variability:

Participants will be asked in advance if they have a history of skin allergy to adhesives to avoid provoking any skin irritation or rash. However, some redness from the adhesive on the ECG surface electrodes may temporarily appear.

Neuro-stimulation:

Overall risks/ discomforts involved are very minimal – Rare (event rate 1% - < 5%)

Possible risks/discomforts may involve:

- a. Discomfort upon insertion of the electrodes for < 5 minutes - Rare (event rate 1% - < 5%)
- b. Discomfort at the lead placement site > 5 minutes – Rare (1 % - < 5%)
- c. Bleeding at the electrode site if the neurovascular bundle is penetrated - Rare (event rate 1% - < 5%)
- d. Localized discomfort if the electrodes should become dislodged during the wearing of the device - Rare (event rate 1% - < 5%)
- e. Localized dermatitis - Rare (event rate 1% - < 5%)
- f. Drop in blood pressure - Rare (event rate 1% - < 5%)

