- g. Syncope (fainting) - Rare (event rate 1% - < 5%)

Adverse effects to supporting personnel

- a. Skin piercing with percutaneous needles - Rare (event rate 1 % - < 5%)

**In our recently completed randomized trial of auricular neuro-stimulation for functional abdominal pain there were no significant or serious adverse events noted. Of 115 enrolled subjects, 10 reported side effects for following reasons, none of which were serious: ear discomfort n=6 (three active/three placebo device); adhesive allergy n=3 (one active/two placebo); syncope due to needle phobia n=1 (placebo).

Safety Monitoring Plan

All procedures will be performed by trained professionals within the standard of care under continuous medical supervision in the hospital setting (research unit). Side effects will be inquired about and documented every week during the study and at the post-study follow-up visit. If any serious harm or discomfort is identified by the subjects or the study personnel, the treatment will be discontinued. Any patient with worsening in symptoms

during the study will be able to drop out at any time and receive standard of care medical therapy. The skin of the external ear will be carefully disinfected to avoid any infection risks. Subjects will undergo vital sign screening before enrollment and vital sign assessment before EAD placement.

Safety Analysis Plan

There are no dangerous interventions related to this study, and the short study timeline allows for discontinuation of treatment when it is proven to be ineffective.

I. PROVISION FOR THE PROTECTION OF PRIVACY OF SUBJECTS AND TO MAINTAIN THE CONFIDENTIALITY OF DATA

All research projects that collect electronic data must use appropriate security measures to ensure that data is protected from theft or loss in order to prevent breaches of confidentiality. You must indicate what encryption tools (or why they are not necessary) from the options below. The IRB will not review this protocol unless you indicate the encryption tools being used to secure your research data. If you do not have encryption in place on your systems, please contact your Information Systems support to arrange for one of the encryptions options listed below.

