Missing Data: Every effort will be made to avoid missing data. Using logistic regression, the pattern of missing data will be explored. Assuming the data are missing at random (MAR) multiple imputations for items will be used. Data analysis overview: Summary statistics, such as mean, median, standard deviation, range and correlation will be used as a first step to examine data. To satisfy parametric assumptions, we may perform transformations with justifications if possible and otherwise use non-parametric tests. We will use CART and biological and physiological information to identify interactions when formulating regression models. Statistical software employed for data analysis will be: Cytel StatXact, SAS version 9.4, Salford System CART for trees, SPSS Version 24. The power calculation was made using PASS 13.

Power

This is not applicable due to this being an exploratory pilot study. This study will be supported by a \$12000 from CTSI (if approved), and number of subject was based on budget.

We will similarly analyze the change in vagal tone at visit 1, visit 4 and visit 5 and the different variables of mitochondrial bioenergetics including basal respiration, ATP production, maximal respiration, spare respiratory capacity and extracellular respiration.

We will also compare cytokines at visit 1; 4 and 5 and if possible correlate the change in cytokines to changes in hfHRV and RMSSD.

J. PROVISIONS FOR MONITORING DATA TO ENSURE THE SAFETY OF SUBJECTS; AND ADDITIONAL SAFEGUARDS TO PROTECT THE RIGHTS AND WELFARE OF SUBJECTS WHO ARE LIKELY TO BE VULNERABLE

The PI will monitor the health of all patients in the study per standard clinical practice. The PI will monitor protocol adherence and supervise data collection, entry, and analysis.

K. ANTICIPATED BENEFITS ASSOCIATED WITH THE PROTOCOL TO HUMAN RESEARCH PARTICIPANTS AND SOCIETY

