Expected adverse events that are not serious will be reported on the Continuing Review Progress Report. Continuing Review will be performed on a 12-month cycle, starting at time of protocol's initial approval. More frequent progress reports will be submitted at the request of the IRB.

Serious Adverse Events: The PI, within 24 hours, will report all serious adverse events occurring in any enrolled subjects to the IRB. Unexpected (but not serious) adverse events occurring in enrolled subjects which, in the opinion of the PI, are possibly related to participation in the protocol will be reported by the PI within 5 working days to the IRB.

Unanticipated problems involving risks to subjects or others will be reported to the IRB within 24 hours.

M. IS THERE A DATA SAFETY MONITORING BOARD IN PLACE? WHO ARE IT'S MEMBERS? HOW OFTEN DO THEY MEET?

As this is a low risk protocol, no data safety monitoring board will be appointed unless requested.

N. DESCRIBE HOW THE CONSENT PROCESS WILL TAKE PLACE. INCLUDE A LIST OF APPROPRIATELY TRAINED PERSONNEL WHO WILL BE INVOLVED.

Written informed consent for participation will be obtained from the parents and children for their child's participation. Written assent will be obtained from youth 12 and 13 years of age using the CHW assent form. Patients ages 14 and above will sign the assent line on the consent form per CHW policy. Consent will be obtained by a study investigator or member of the research team at the patients' appointment in the GI Clinic. Volunteers' consent will allow for accessing information collected for program evaluation/clinical purposes. Participating children and parents will have the option of having the consent/assent document read aloud to them to facilitate understanding. Copies of signed consent/assent documents will be given to participants. When consent is given for a minor child to participate in a research study by one or both parents, and the child reaches the age of majority (18 years) the child will be re-consented as an adult to continue participation in the study. If age of majority is reached while the participant is active and continues to receive study interventions per the study protocol, he/she will be re-consented using the most current approved IRB informed consent document and HIPAA form. If age of majority is reached after all study interventions have been completed and

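### Scheduled safety questions ask about side effects rather than any health problem, so non-serious events that subjects do not link to treatment may be missing from the adverse-event incidence

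*Combined protocol and SAP*

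**What the plan says.** Three places describe scheduled safety questioning:

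- **Measurements and Data Collection (section F):** at each device placement, staff ask and document "if subjects experienced any side effects from the EAD during the previous week".
- **Study Design Overview (section D):** "Subjects will be screened weekly for any side effects by registered nurses".
- **Safety Monitoring Plan (section H):** "Side effects will be inquired about and documented every week during the study and at the post-study follow-up visit".

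Other routes exist:

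- The Study Design Overview adds that "All subjects will be asked to notify the PI or research team with any worsening in symptoms or side effects of therapy".
- The Safety Monitoring Plan covers the case "If any serious harm or discomfort is identified by the subjects or the study personnel".
- Section J states: "The PI will monitor the health of all patients in the study per standard clinical practice".
- Section L has every serious adverse event in an enrolled subject go to the IRB, whatever its cause.

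The outputs are worded more widely than the questions. Safety Data (section H) states: "Incidence of adverse events will be summarized by treatment". For events that are unexpected but not serious, section L reports those which, "in the opinion of the PI, are possibly related to participation in the protocol will be reported by the PI within 5 working days". The term adverse event is not defined.

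**The concern.** An incidence of adverse events should count every untoward event, with cause assigned afterwards by someone qualified to judge it. Here the scheduled questions carry a causal filter. Asking an adolescent aged 12 to 18 about side effects, and at placement visits about side effects of the ear device in particular, invites an answer limited to what the subject already blames on treatment. The PI can judge relatedness only for events that were recorded.

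The events most exposed are non-serious ones with no obvious link to the ear: dizziness, faintness away from the research unit, or a reaction to the blood draw that appears later. Some are plausible here. The protocol's own list of neuro-stimulation risks includes a fall in blood pressure and syncope. About 50 ml of blood is mentioned for collection at Visits 1, 4 and 5, but blood-draw reactions are not among the listed risks.

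At stake is the credibility of the safety summary. The study is classed as above minimal risk in minors, has no data safety monitoring board, and has only 7 subjects, so each missed event counts.

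**Working it through.** The plan gives no figure to reproduce. The sample size of 7 is budget-based and power is declared not applicable. The check is mainly a comparison of wording.

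**Step 1. Input against output.**

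| Place | Route | Does the wording imply a cause? |
|---|---|---|
| Measurements and Data Collection | Scheduled, at each placement | Yes, the device |
| Study Design Overview, nurse screening | Scheduled, weekly | Yes, by the term side effects; not limited to the device |
| Safety Monitoring Plan | Scheduled, weekly and at follow-up | Yes, by the same term; not limited to the device |
| Study Design Overview, request to notify | Volunteered by subject | Not for symptom worsening |
| Safety Monitoring Plan, harm identified by staff | Observation | No, but limited to serious harm or discomfort |
| Section J, PI oversight | Usual clinical practice | No, but no set question |
| Section L, serious events | Reporting rule | No |
| Section H, Safety Data | **Output:** incidence of adverse events | No |

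Every scheduled question implies a cause, and the output does not. The cause-neutral routes cover serious events, volunteered worsening and what staff see. The remaining gap is non-serious events that occur out of staff's sight and are neither blamed on treatment nor thought of as a worsening of symptoms.

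**Step 2. Timing.** The device-specific question is tied to placement, and Table 1 shows the last placement at Visit 4. Visit 5 falls about 2 to 3 months after the last device is removed. Only the Safety Monitoring Plan's general wording extends enquiry to that visit. At Visit 1 a question about the previous week's device effects has no content, so there is no baseline answer to the same question. Medical history and co-morbid symptoms are recorded beforehand, but not in a form that matches the later enquiry.

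**Step 3. Direction and size.** Let *p* be the true share of subjects with an event and *c* the share captured. The expected recorded incidence is *c* × *p*, so any *c* below 1 biases it downward. The documents give no value of *c* and do not show that it is below 1.

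For illustration only, with independent subjects: expected number recorded = 7·*p*·*c*; chance of recording at least one affected subject = 1 − (1 − *p*·*c*)^7.

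| *p* | Basis | *c* = 1 | *c* = 0.75 (assumed) | *c* = 0.5 (assumed) |
|---|---|---|---|---|
| 5% | Upper end of the range given for each listed device risk | 30.2% | 23.5% | 16.2% |
| 8.7% | 10/115 with side effects in the team's earlier trial, both arms | 47.1% | 37.6% | 26.7% |
| 20% | Assumed | 79.0% | 67.9% | 52.2% |

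Example: *p* = 10/115 = 0.087 and *c* = 0.5 give 1 − (1 − 0.0435)^7 = 0.267, and the expected number falls from 7 × 0.087 = 0.61 to 0.30. The 10/115 is itself a count of reported side effects, so it is only a placeholder for *p*.

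**Step 4. What n = 7 alone implies.** For 0/7 the upper 95% limit is 1 − 0.05^(1/7) = 34.8% one-sided, or 1 − 0.025^(1/7) = 41.0% two-sided. These limits would be the same with perfect questioning. They say nothing about under-recording.

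**The case against.** The strongest reply is that the plan does not depend on one narrow question. Only the Measurements and Data Collection section restricts the enquiry to the device. Nurses screen for any side effects, subjects are asked to report any worsening, staff can identify harm, and the PI oversees everyone's health. Procedures take place in the research unit under medical supervision, so faintness during a blood draw there would be seen. The data collection forms are not in the documents, and their wording may be broader. Safety is not the aim of this budget-sized mechanistic pilot, and with 0.61 affected subjects expected at the earlier trial's rate, losing half changes the count by about 0.30 of a subject.

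Much of this stands, and it rules out three stronger readings that a reader might infer:

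- **That the subject alone decides causality before anything is recorded.** Staff observation, volunteered worsening and the all-cause rule for serious events contradict this.
- **That nothing is asked before treatment.** Medical and psychological history, co-morbid symptoms and vital signs are all collected. What is missing is a baseline answer to the same question.
- **That the incidence will be an undercount of some stated size, say 30% to 70%.** Any such range only restates an assumed capture rate.

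What the reply does not remove is that the protocol describes no cause-neutral scheduled question, although its output is worded as all adverse events. The additional routes are volunteered, observational or unspecified. None is a uniform documented enquiry for non-serious events away from the unit.

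**Conclusion.** The point holds as a risk of under-recording confined to non-serious events that subjects do not attribute to treatment and that staff do not see. Any bias is downward, and its size cannot be estimated from the documents. The conclusion rests on two assumptions: that adolescents hear side effects as meaning effects of the treatment, and that the forms, which are not shown, follow the protocol's wording.

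This is an inexpensive improvement to a safety summary that will be imprecise in any case. It does not threaten the mitochondrial, HRV or cytokine results.

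**What to change.** 1. In the Study Design Overview, Measurements and Data Collection, and the Safety Monitoring Plan, replace the differing wordings with one open, cause-neutral question, for example: *any new or worse health problem since the last visit?*
2. Add a yes/no checklist of the neuro-stimulation risks a to g already listed in section H, plus blood-draw reactions.
3. Ask both at Visit 1 before the first device, as a like-for-like baseline added to the history already taken, and at every later visit including Visit 5. At Visit 1, refer the question to a stated recent period, since there is no earlier device visit.
4. Define adverse event once, and have the PI record relatedness separately for each event.
5. In Safety Data, report all events and related events separately as n/7, and remove the phrase about summarizing by treatment, since there is one arm.

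The cost is a revised form item, edits to the sections named, a few minutes at visits already in Table 1, and a longer list of mostly unrelated events for the PI to classify. No extra visit is needed and treatment does not change.

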We have found in 59 subjects (30 healthy controls -HC; 29 FGID) with no difference in age (HC: median 16.3, range 10.9-18.7 yrs; FGID median 15 range 13-18 yrs; $p = 0.088$), basal respiration (BCR), extracellular acidification rate (ECAR –non-mitochondrial respiration) and ATP production in patients with FGID were about half the values found in HC. These findings could explain the severe fatigue and multi-system involvement in FGID subjects. We have also found that vagal function is decreased. Real-time vagal activity can be indexed using heart rate variability (HRV) parameters, particularly high frequency (hfHRV), root mean square of successive differences (RMSSD) and heart rate recovery after exercise. These measures are well accepted as reflecting an individual's "vagal health" (1). A cross sectional meta-analysis of 11 articles of adult subjects with IBS (8) showed decreased vagal modulation with increased sympathetic tone. Low vagal modulatory activity occurs in other chronic pain conditions (9-13), and has been linked with poor adaptive behavior in a meta-analysis of 44 studies in 5000 children (14). In turn, poor adaptability and high pain severity in childhood more likely results in pain-related FGID, non-abdominal chronic pain, and co-morbid anxiety and depression in adulthood (15). We prospectively studied the changes in HRV in our clinic in 13 subjects who had 2 visit points (7 with improvement in the Functional Disability Inventory –FDI- and 5 with either no improvement or worsening). RMSSD from supine (33.14 ± 11.06 ms) and from standing (11.39 ± 3.37 ms) increased in the pFGID improved group (supine 59.11 ± 25.04 ms, standing 38.40 ± 21.69 ms). RMSSD from supine dropped in the group that did not improve. Comparison of RMSSD difference between 1st and 2nd visit supine showed a trend for a difference between the two groups ($p=0.09$).

The relationship between mitochondrial bioenergetics and vagal modulation in the cardiovascular arena is nicely summarized by He et al al (1) (FIG 1). Direct vagal stimulation provides the clearest evidence of this relationship. Vagal stimulation improves cardiac function in experimental congestive heart failure and after ischemic injury,

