the participant remains in the study for purposes of data collection for outcomes only a separate “Age of Majority” informed consent will be obtained.

O. PROCEDURES TO BE EMPLOYED IN ANALYZING DATA AND THE ANTICIPATED SIGNIFICANCE OF THE PROPOSED STUDY

Analyses will be conducted with SPSS and SAS software programs. Probability levels of < .05 will be used as cut offs for statistical significance.

The key significance of this study is the identification of a reduction in inflammatory cytokines, and increase in hfHRV. With this study, we hope to lay the foundation for the application of AED for pediatric functional GI disorders by demonstrating improvement in mitochondrial bioenergetics and reduction in inflammation as part of the pathophysiology. This is an innovative and novel understanding of the pathophysiology of FGID, which will enhance our knowledge on the brain-gut neural connectivity underlying functional disorders and ultimately improve patient care.

P. FINANCIAL RELATIONSHIPS

The EAD devices will be supplied by the distributing company (IHS) at manufacturing rate. A grant from Advancing a Healthier Wisconsin (AHW) will partially support this proposal and a CTIS Start Up Pilot award (\$12000) funding decision is pending. Patients will receive a stipend of \$20 at each of the following visits: Visit 1, Visit 4 and Visit 5. (After each blood draw is completed)

Q. ADVERTISEMENTS / FLIERS

Not applicable.

R. BIBLIOGRAPHY

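### The plan names RMSSD as the primary HRV outcome without fixing a posture, and its statement of significance names hfHRV, so the vagal claim has no single pre-specified measure

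*Combined protocol and SAP*

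**What the plan says.** The Heart Rate Variability section, under Measurements and Data Collection, lists what will be analysed: "HRV indices such as high and low frequency domains, low/high frequency ratio and the time domain RMSSD as a surrogate of vagal tone". It then ranks them: "The RMSSD values will be the primary HRV outcome". The values are to be "compared to baseline (pre-EAD stimulation), post-stimulation and 2-3 month later at follow up". Each recording is split, "five minutes supine and 5 standing", with the reason given as "Recordings will be performed supine and standing to assess baroreflex response". No posture is attached to the primary RMSSD value, and neither post-baseline time point is named as the main one.

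The analysis text, under the Power heading, says "We will similarly analyze the change in vagal tone at visit 1, visit 4 and visit 5". It gives no index and no posture there. It then plans to correlate cytokine changes with both hfHRV and RMSSD.

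Section O sets a significance cut-off of .05 and continues: "The key significance of this study is the identification of a reduction in inflammatory cytokines, and increase in hfHRV". RMSSD does not appear in that section. The documents give no sidedness, testing order or multiplicity rule.

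**The concern.** The study's argument is a chain: the device raises vagal tone, and the rise in vagal tone improves mitochondrial bioenergetics and lowers inflammation. There are seven subjects and no control arm, so the reading of the mitochondrial and cytokine results leans on whether the first link was seen.

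The plan identifies that link by RMSSD in one place and by hfHRV in another, and each can be read supine or standing. A report could follow the text and present a rise in hfHRV alone, or in standing RMSSD alone, as the vagal result. A mixed HRV picture could then pass as confirmation of the mechanism, and the other outcomes would be interpreted against a rise that the named primary measure may not have shown.

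**Working it through.** **No planned figure to reproduce.** The protocol gives no power calculation or effect size. The number of subjects, 7, was set by budget. The only stated operating figure is the .05 cut-off in Section O.

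**Do other sections settle index and posture?**

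| Place | Index | Posture |
|---|---|---|
| Heart Rate Variability section | RMSSD primary; HF, LF and LF/HF also analysed | both recorded, none chosen |
| Analysis text under Power | vagal tone; hfHRV and RMSSD for correlations | none |
| Section O | hfHRV | none |

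They do not. Because RMSSD is called a surrogate of vagal tone, the analysis text may mean RMSSD. That still leaves posture open and leaves Section O on a different index.

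**Number of readings.** Two indices (RMSSD, hfHRV) × two postures = 4 tests at Visit 4. Counting Visit 5 as well gives 8.

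**Chance of at least one nominally significant result when nothing changes**, independent tests:

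- Two-sided .05, increases only (.025 each): one test 2.5%; four tests 1 − 0.975^4 = 1 − 0.9037 = 9.6%.
- Two-sided .05 with either direction counted, or one-sided .05 with increases counted: one test 5%; four tests 1 − 0.95^4 = 1 − 0.8145 = 18.5%.
- Eight tests: 1 − 0.975^8 = 18.3% for increases only; 1 − 0.95^8 = 33.7% for either direction.

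RMSSD and hfHRV come from the same ECG segment, so independence is an upper reference. Paired t-tests with n = 7 were simulated under assumed correlations that the documents do not give: 0.5 to 0.9 between indices, 0.3 to 0.7 between postures, and 0.5 between the two time contrasts. The .05 tests are two-sided.

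| Tests | Increases only | Either direction |
|---|---|---|
| 1 | about 2.5% | about 5% |
| 4 (Visit 4) | 6.2% to 8.8% | 12.5% to 17.5% |
| 8 (Visits 4 and 5) | 11.1% to 15.6% | 22.2% to 30.2% |

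**Do the postures disagree in the team's own data?** Section C gives RMSSD in the clinic patients who improved:

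- Supine: 59.11 − 33.14 = 25.97 ms, or 25.97/33.14 = +78%.
- Standing: 38.40 − 11.39 = 27.01 ms, or 27.01/11.39 = +237%.

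The absolute rises are nearly equal and in the same direction. The percentages differ because the standing baseline is lower. For the between-group comparison, Section C reports supine only: "Comparison of RMSSD difference between 1st and 2nd visit supine showed a trend for a difference between the two groups".

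**Would adjusting afterwards work instead?** With n = 7 the smallest two-sided exact signed-rank p-value is 2/2^7 = 2/128 = 0.0156. That is below a two-test Bonferroni cut of 0.025 but above the four-test cut of 0.0125. An exact signed-rank analysis of four readings could not reach significance after Bonferroni adjustment, whatever the data. Choosing one measure beforehand is the more workable remedy.

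**The case against.** Section O is a narrative of what the team hopes to show. It sets no test or decision rule, and the only passage that ranks the HRV indices chooses RMSSD. Sections C and F present hfHRV and RMSSD as indicators of the same vagal activity, so hfHRV in Section O may be loose shorthand for vagal tone. The design is an exploratory pilot that could not support a confirmatory vagal claim whichever measure were chosen, and the specific aim concerns bioenergetics and inflammation.

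Most of this stands, and it limits the point. A reader might infer that the plan has a formal success criterion on hfHRV that competes with RMSSD; it has not. A reader might also take the 78% and 237% rises as proof that the postures give conflicting answers. The near-equal absolute changes do not support that, and Section C does not say that those patients received the device. The split between a supine recording for resting tone and a standing one for the baroreflex is also an inference, since the text assigns both recordings together to the baroreflex response and both follow a ten-minute rest.

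What the objection leaves untouched is that the plan names a primary HRV outcome and a significance cut-off, does not fix the posture, and names a different index where it says which HRV finding matters.

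**Conclusion.** The point holds as an unresolved choice of measure. The vagal-mechanism claim could be made on either index in either posture, and no section reconciles them. For four two-sided .05 tests the chance of at least one false significant increase is at most about 9.6%, against 2.5% for one fixed test. The figure of 18.5% against 5% applies only if either direction counts or the tests are one-sided. A reader might quote 18.5% as the chance of a false claim of increase; under two-sided testing it is not. These ceilings take the tests as independent; positive correlation lowers them. Sidedness and correlations are assumptions here, because the documents give neither.

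Severity is minor to moderate. The study is an exploratory pilot of seven, and RMSSD is primary among HRV measures only, so the weakness bears on the mechanistic interpretation and leaves the specific aim itself unchanged.

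**What to change.** In the Heart Rate Variability section, name one primary HRV comparison in advance: one index, one posture, one time contrast. Supine RMSSD is the natural choice, because that section ties vagal output to resting HRV and the between-group comparison in Section C was supine. This is a judgement; what matters is that a single measure is fixed beforehand. Make the analysis text under Power and the significance statement in Section O refer to that measure. Label standing RMSSD, hfHRV, LF and LF/HF as supportive and exploratory. State whether tests are one- or two-sided.

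If Visit 1 to Visit 4 is the contrast, a further point needs attention. Protocol and Procedures (Section D) has HRV measured before device placement at Visit 1 but after placement at Visit 4. The contrast then mixes any acute effect of placement with that of the treatment course. Either say so in the plan or make the timing the same at both visits.

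The cost is a few sentences and no additional data, plus a change to one measurement time if the visits are aligned. The team gives up the freedom to present an isolated hfHRV or standing change as the vagal result.
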